5.3.2.3. Rituximab: Overdose

There has been no experience with overdose in human clinical trials. The highest intravenous dose of rituximab tested in humans to date is 5000 mg (2250 mg/m^2), tested in a dose escalation study in subjects with chronic lymphocytic leukemia. No additional safety signals were identified (MabThera[®] SmPC 2023).

Subjects who experience overdose should have immediate interruption of their infusion and be closely monitored (MabThera[®] SmPC 2023).

In the postmarketing setting, five cases of rituximab overdose have been reported. Three cases had no reported adverse event. The two adverse events that were reported were flu-like symptoms, with a dose of 1.8 g of rituximab and fatal respiratory failure, with a dose of 2 g of rituximab (MabThera[®] SmPC 2023).

Refer to Section 11.3 for further information regarding special reporting situations as a result of overdose.

5.3.2.4. Rituximab: Dose Modification for Rituximab-Related Adverse Reactions

At the investigator's discretion, the rituximab dose should be held for any unmanageable, potentially rituximab-related toxicity that is consistent with the regional prescribing information and the rules outlined in this section. Rituximab should be held for any rituximab-related Grade 4 toxicity or for any, clinically significant, unmanageable potentially rituximab-related non-hematological Grade 3 adverse events. Rituximab may be held for a maximum of 28 consecutive days for a rituximab-related toxicity, unless reviewed and approved by the Medical Monitor.

The dose of rituximab should be modified according to the dose modification guidelines in [Table 6](#) if any Grade 4 or unmanageable non-hematologic Grade 3 toxicity attributed to rituximab occurs. Dose modifications of rituximab must be recorded in the case report form (CRF).

Table 6. Rituximab: Dose Modification for Toxicity

Occurrence	Action to be Taken
First, Second, Third	Withhold rituximab until recovery to Grade ≤ 1 or baseline; may restart at original dose level
Fourth	Discontinue rituximab ^a

- a. If rituximab is discontinued for toxicity prior to the completion of induction treatment (Cycle 1), the subject will discontinue study drug and be followed for progression. If rituximab is discontinued for toxicity during the maintenance phase, the subject may continue on study drug.

Note: for guidance on management of rituximab in relation to infusion reactions see [Section 5.3.2.5](#).

A missed dose of rituximab during the induction phase in Cycle 1 for any reason will not be made up (i.e., the dose will be skipped) during Cycle 1; the visit window for Cycle 1 is ± 3 days.

- If the subject skips dosing of rituximab during Cycle 1 due to reasons other than not being able to tolerate rituximab, subject can make up the induction phase dosing as soon as possible during Cycle 2 as long as there is a minimum of 5-day window between doses and 5-day window prior to Cycle 3 Day 1.
- If induction phase cannot be completed prior to 5 days of Cycle 3 Day 1, subject can begin maintenance rituximab dosing according to the protocol schedule if only one induction phase dose is missed. If more than one induction phase dose is missed, please contact PCYC Medical Monitors for further guidance.

A missed dose of rituximab during the maintenance phase in Cycles 3-25 may be given within the defined visit window (i.e., ± 3 days for Cycle 3 and ± 7 days for Cycles 5-25).

If rituximab dosing is delayed for toxicity that does not require study drug (ibrutinib/placebo) to be held for toxicity, administration of study drug should continue at the investigator's discretion. If a rituximab infusion is delayed due to scheduling delays, administration of study drug should continue.

Any other clinically important events where dose delays may be considered appropriate by the Investigator must be discussed with the Medical Monitor.

Upon recovery, subjects should resume the protocol-specified treatment schedule as soon as possible.

5.3.2.5. Rituximab: Dose Interruption for Infusion-Related Reactions

Modify administration of rituximab for infusion-related reactions of any severity as described below.

- For Grade 1 and 2 infusion-related reactions, slow the infusion rate by a minimum of 50% and monitor subject closely. Provide medical intervention as indicated. If symptoms resolve, complete the infusion at the decreased rate. If symptoms do not improve, or worsen, discontinue the infusion.
- For Grade 3 infusion-related reactions, interrupt the infusion, provide medical intervention as appropriate. Monitor subject closely and if symptoms resolve resume the infusion at 50% or less of the previous rate. If there is no return of symptoms, then complete the infusion at the decreased rate. If symptoms do not improve, or worsen, discontinue the infusion.
- For Grade 4 infusion-related reactions, stop the infusion. Provide appropriate medical intervention. Contact the Medical Monitor prior to re-challenge or if permanent discontinuation of rituximab is necessary.

5.3.2.6. Rituximab: Dose Reduction

There will be no dose reductions for rituximab. Particular attention should be paid to the Warnings and Precautions sections of the product label.

5.3.2.7. Rituximab: Dose Discontinuation

Rituximab should be discontinued in the event of a rituximab toxicity requiring a dose hold lasting more than 28 days, unless reviewed and approved by the Medical Monitor. If rituximab is discontinued for toxicity prior to the completion of induction treatment (Cycle 1), the subject will discontinue study drug (ibrutinib/placebo) and be followed for progression. If rituximab is discontinued for toxicity during the maintenance phase, the subject may continue on study drug.

5.4. Study Treatment Compliance**5.4.1. Study Drug (Ibrutinib/Placebo) Compliance**

The study drug (ibrutinib/placebo) is to be prescribed only by the Principal Investigator or a qualified physician or other licensed prescriber listed as a Sub-Investigator on the Form FDA 1572/Investigator Information and Agreement (IIA). The study site personnel must maintain all study drug records in the study file, and record all study drug's dispensing and returning on the drug accountability form and in the subject's source documents. The study drug must not be used for any purpose other than that outlined in this protocol, including other human studies, animal investigations, or in vitro testing. The IXRS will be used to assign study drug kits for each subject enrolled with each cohort assignment.

Drug supplies for each subject will be inventoried and accounted for throughout the study by the site personnel. Subjects will be provided with a subject diary card at the beginning of Day 1 of each cycle to record daily dosing. The site personnel must instruct the subjects to bring the completed subject diary card along with any used and unused study drug to each study visit. The site personnel must reconcile and document the returned capsules from the study subjects at each study visit to ensure compliance with study drug administration. Instructions for self-administration and storage conditions of study drug will be provided to the subjects by the site personnel. Precautions associated with the use of study drug and prohibited concomitant medications must be reviewed with the study subjects by the Investigator or qualified study site personnel. The site staff will provide additional instruction to re-educate any subject who is not compliant with the study drug dosing schedule.

5.4.2. Rituximab Compliance

Rituximab treatment will be administered by qualified study-site personnel. The site pharmacist or designee must document all rituximab treatment and premedications prepared for the infusion and administration in the subject's source documents. Drug supplies for each subject will be inventoried and accounted for throughout the study by the site personnel as appropriate. The infusion will be administered to the study subjects according to the approved prescribing information per protocol and/or institutional guidelines.

5.5. Criteria for Permanent Discontinuation of Study Treatment

Investigators are encouraged to keep a subject who is experiencing clinical benefit in the study unless significant toxicity puts the subject at risk or routine noncompliance puts the study outcomes at risk. For a complete list of criteria for permanent discontinuation of study treatment, refer to Section [9.2](#).

An End of Treatment Safety Follow up visit (Section [8.2.3](#)) is required for all subjects except for those subjects who have withdrawn full consent.

5.6. Replacement of Subjects

If a subject discontinues study treatment at any time, the subject will not be replaced.

6. CONCOMITANT MEDICATIONS/PROCEDURES

Concomitant therapies must be recorded from the time of ICF signing and recorded continuously from the time of signing the ICF to 30 days after the last dose of study treatment.

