5.3.1.4. Ibrutinib/Placebo: Dose Modification for Ibrutinib/Placebo-Related Adverse Reactions

For an ibrutinib/placebo-related adverse reaction, the recommendations for dose modification of ibrutinib/placebo are provided in [Table 4](#) and [Table 5](#) if any of the following hematologic or non-hematologic toxicities occur:

- Grade 3 or greater neutropenia with infection or fever
- Grade 4 neutropenia (ANC<500/ μ L) for more than 7 days. See Section [6.1](#) for instructions regarding the use of growth factor support.
- Grade 3 thrombocytopenia (platelets<50,000/ μ L) in the presence of clinically significant bleeding events.
- Grade 4 thrombocytopenia (platelets<25,000/ μ L).
- Grade 3 or greater non-hematological toxicity (Note: [Table 5](#) recommendations for Grade 3 or higher cardiac failure and cardiac arrhythmias)
- Grade 2 cardiac failure ([Table 5](#))
- Any other Grade 4 or unmanageable Grade 3 hematological toxicity.

If clinically indicated, the use of anticoagulants or antiplatelet agents may be considered for the thromboprophylaxis of atrial fibrillation (Section [6.2.3](#)).

For other grade 3 or 4 AEs, and grade 2 AEs that are deemed per the investigator potentially manageable by dose reduction, these can be managed with a one dose level dose reduction.

In the event that the investigator feels deviation from the recommendations above is required, please consult the Medical Monitor to discuss.

If administration of study drug is delayed or discontinued for toxicity that does not require rituximab to be held for toxicity, rituximab dosing should continue at the investigator's discretion.

Study drug should be discontinued in the event of a toxicity considered to be related to study drug requiring a dose hold lasting more than 28 days, unless reviewed and approved by the Medical Monitor.

Dose changes must be recorded in the Dose Administration eCRF.

Table 4. Ibrutinib/Placebo: Study Drug Dose Modifications for Events not Specified in Table 5

Occurrence	Action to be Taken
First	Withhold study drug until recovery to Grade \leq 1 or baseline; may restart at original dose level (ie, 4 capsules [560 mg/day]) ^a
Second	Withhold study drug until recovery to Grade \leq 1 or baseline; may restart at 1 dose level lower (ie, 3 capsules [420 mg/day])
Third	Withhold study drug until recovery to Grade \leq 1 or baseline; may restart at 1 dose level lower (ie, 2 capsules [280 mg/day])
Fourth	Discontinue study drug

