7.1.1.6. Prior and Concomitant Medications

All active medications from the signing of ICF through 30 days after the last dose of study treatment will be documented.

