# 1 INTRODUCTION

The statistical analysis plan (SAP) version 7.0 is based on the protocol amendment 4 dated February 07, 2023. This SAP defines key elements including variable definitions, and statistical methods for analysis of data in evaluation of efficacy and safety of PCYC-1141-CA. Analyses of biomarker and pharmacokinetics (PK) data are not in the scope of this document.

[figure not shown]
Throughout this SAP, "study treatment" and "study drug" are used interchangeably, and both are referring to ibrutinib, placebo, and/or rituximab.

Analysis methods specified in this document take precedence over those described in the protocol should there be any differences.

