#### 3.3 Concomitant Medications

Medications will be coded to Anatomical Therapeutic Chemical (ATC) class and the preferred drug name (hereafter referred as "preferred name") per World Health Organization (WHO) drug dictionary.

Concomitant medications will be summarized by ATC class and preferred term (PT) for each treatment arm in the safety population. The summarization includes all the concomitant medications taken at any time while on study treatment (i.e., from the date of first dose through the date of last dose of the study treatment). Each subject will be counted once for each PT, and each ATC class. The following concomitant medications will be summarized separately.

- CYP3A inhibitors and inducers
- Anticoagulants and antiplatelet agents
- Blood supportive products and immunoglobulin
- Growth factors

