## 5 SAFETY ASSESSMENTS

Safety data will be summarized by treatment for the safety population unless otherwise indicated. [Table 7](#) summarizes the safety analyses to be carried out. AEs will be coded in accordance with the Medical Dictionary for Regulatory Activities (MedDRA). Severity of AEs will be graded by the investigator according to the NCI Common Terminology Criteria for Adverse Events (NCI-CTCAE) v4.03.

The treatment-emergent period is defined as the period from the date of the first dose of study treatment up to 30 days after the date of the last dose of study treatment or the day before initiation of subsequent anti-cancer therapy, whichever comes first.

The treatment-emergent adverse events (TEAEs) are those events that occur or worsen during the treatment-emergent period or that are related to the study treatment. TEAEs or deaths related to COVID-19 infection will be summarized or listed separately. All laboratory values will be converted to and reported as international standard (SI) units. In general, only data from the central laboratory will be summarized and analyzed. When central lab values are missing and local lab values are available, local lab values will be used. Laboratory parameters will be graded using the NCI CTCAE v4.03. Unless otherwise specified, only baseline and post-baseline values collected during the treatment-emergent period will be included in the safety analysis.

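### SAP 3.3 closes the blood-product and growth-factor tables at the last dose, while the adverse events they treat are counted for up to 30 more days

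*Protocol*

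**What the plan says.** **Collection.** Protocol Section 6 has concomitant therapies "recorded continuously from the time of signing the ICF to 30 days after the last dose of study treatment". Protocol 7.1.1.6 repeats the window: "All active medications from the signing of ICF through 30 days after the last dose of study treatment will be documented". The Schedule of Assessments (Protocol Appendix A) agrees, and the safety follow-up visit in Protocol 8.2.3 includes a review of concomitant medications.

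**Medication tables.** SAP 3.3 summarises what was taken on study treatment, which it spells out as "from the date of first dose through the date of last dose of the study treatment". It then names four classes for separate summary: CYP3A inhibitors and inducers, anticoagulants and antiplatelets, "Blood supportive products and immunoglobulin", and "Growth factors". No separate window is given for these four, so they take the one just stated.

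**Adverse events and laboratory values.** SAP Section 5 runs the treatment-emergent period from first dose "up to 30 days after the date of the last dose of study treatment", or to the day before subsequent anti-cancer therapy if that is sooner. Post-baseline laboratory values come from the same period unless otherwise specified.

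**Terms and precedence.** The SAP Introduction defines study treatment and study drug together, saying "both are referring to ibrutinib, placebo, and/or rituximab". It also gives the SAP precedence over the protocol on analysis methods, so the narrower window governs.

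**The concern.** The two supportive-care tables and the adverse event tables describe the same toxicities over different periods. A cytopenia or bleed arising at or after the last dose is counted, with its grade, for up to 30 days. The transfusion or growth factor given for it is not counted if first use falls after the last dose. Protocol 11.4.8 makes the mismatch visible: a bleed requiring red-cell transfusion must be reported as Grade 3 or higher and so counts as major hemorrhage. The SAP could therefore report the event while leaving out the transfusion that fixed its grade.

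At stake is whether a reader of the study report can reconcile these tables with the safety tables. If toxicity stops are more common in one arm, supportive-care use could also be understated by different amounts in the two arms.

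**Working it through.** There is no stated figure to reproduce, because the point is a comparison of date windows.

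**Step 1. The windows, in days after the last dose of study treatment**

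| Item | Source | Days covered |
|---|---|---|
| Medications collected | Protocol 6, 7.1.1.6, Appendix A | 30 |
| Adverse events, laboratory grades | SAP 5 | up to 30 |
| Medications summarised | SAP 3.3 | 0 |

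Up to 30 days per subject are collected but not tabulated. SAP 3.5 covers only subsequent anti-cancer treatment, and no other SAP section picks up the later records. SAP 8.1 does not list the window as a change from the protocol.

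**Step 2. How a record falls in the gap.** Under Protocol 5.3.1.4, study drug is withheld for the listed toxicities. It is to be discontinued for related toxicity "requiring a dose hold lasting more than 28 days", unless the Medical Monitor approves otherwise. If a hold becomes permanent and no other study treatment is given, the last dose is the one before the hold. Days 1 to 28 of the hold then all lie inside the 30 collected days and outside SAP 3.3.

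**Step 3. What limits the loss**
- Study treatment includes rituximab. A subject who stops ibrutinib/placebo but receives rituximab later stays in the window until that dose. After Cycle 25 no rituximab is scheduled, so stopping ibrutinib/placebo then ends all treatment.
- Medication started by the last dose, or ongoing at it, is counted.
- Each subject counts once per preferred term and ATC class, so earlier use keeps the subject in the table.

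**Step 4. Size, by assumption only.** Let d be the share of an arm whose whole study treatment ends for toxicity. Let q be the share of those whose first use of the class falls in days 1 to 30 after the last dose.

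Missed share of an arm = d × q. With a common q, the loss differs between arms by q × (dA − dB).

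The documents give neither d nor q. SAP 1.3 gives 445 randomised and SAP 1.6.2 a 3:1 ratio. 445 × 0.75 = 333.75, so about 334 in Arm A and 111 in Arm B (the tables use the safety population, so these are approximate).

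| Assumed dA, dB | Assumed q | Missed, Arm A | Missed, Arm B | Difference in loss |
|---|---|---|---|---|
| 20%, 20% | 5% to 40% | 1% to 8% | 1% to 8% | 0 |
| 20%, 10% | 5% to 40% | 1% to 8% | 0.5% to 4% | 0.5 to 4 points |
| 30%, 10% | 5% to 40% | 1.5% to 12% | 0.5% to 4% | 1 to 8 points |

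For dA = 30%, dB = 10% and q = 10% to 20%, Arm A loses 0.03 × 334 = 10 to 0.06 × 334 = 20 subjects. Arm B loses 0.01 × 111 = 1 to 0.02 × 111 = 2.

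With dA = 30%, dB = 10%, q = 20% and true use of 30% versus 20%, the table would show 30% − 6% = 24% and 20% − 2% = 18%. A 10-point difference would appear as 6.

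**Step 5. Direction.** The ordering depends on a similar q in both arms. If dA = 20% with qA = 10% (loss 2%) and dB = 10% with qB = 40% (loss 4%), the arm with fewer stops loses more.

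**The case against.** Collecting for longer than a table summarises is not an error. SAP 3.3 states its window openly, and on-treatment use is a coherent reading of concomitant. That stands: the documents do not contradict themselves here. The point is that two descriptive tables would be more useful on the window of the events they relate to.

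A reader might infer four stronger things, none of which the documents support.

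- *That these tables are the plan's measure of cytopenia and bleeding burden.* SAP 3.3 sits under subject information. SAP Table 7 assesses those toxicities through adverse events, events of special interest and worst laboratory grades, all on the longer window. The toxicity signal after the last dose is kept; only the medication count is cut.
- *That all four tables use the wrong window.* Protocol 6.2.1 and 6.2.3 treat CYP3A agents and anticoagulants as matters of exposure and bleeding risk while ibrutinib is taken. Overlap with dosing is the relevant period, and adding later starts would dilute those tables. One can reply that an anticoagulant begun in a hold that becomes permanent is also missed. That is true, but it does not change what the table is for.
- *That the rule removes precisely the care given for events that end treatment.* The limits in Step 3 of the working show that much of it can remain.
- *That the comparison between arms is biased.* With equal stop rates and equal post-dose use the losses are equal, and the documents report neither by arm.

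**Conclusion.** The mismatch holds on the text for the blood-product/immunoglobulin and growth-factor tables. Its certain size is a window of up to 30 days per subject in which records are collected and events counted but supportive care is not tabulated. It bites only when all study treatment, rituximab included, has ended and the subject's first use of that class comes afterwards.

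The number of subjects lost, and the size and direction of any difference between arms, are unknown. The percentages shown are illustrations with assumed inputs. The loss would be larger in an arm with more toxicity stops only if post-dose use per stop is similar in both arms.

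Severity is minor. Protocol 10.5 plans no formal testing of safety data, and no primary or key secondary endpoint or alpha allocation is affected.

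**What to change.** In SAP 3.3, for the blood supportive products/immunoglobulin table and the growth factor table, summarise use during the treatment-emergent period as defined in SAP Section 5. Keep the count from first to last dose as a second column. Leave the CYP3A and anticoagulant/antiplatelet tables on the on-treatment window, and say in the text that this is deliberate.

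The cost is a sentence of SAP text, a second date filter and one extra column in two tables. No new data are needed. The added counts would be expected to be slightly higher, and so less favourable, than the on-treatment ones.

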6.1. Permitted Concomitant Medications

Supportive medications in accordance with standard practice (such as for emesis, diarrhea, etc.) including prophylaxis for infusion-related reactions are permitted. Use of neutrophil growth factors (filgrastim and pegfilgrastim) or red blood cell growth factors (erythropoietin) is

permitted per institutional policy, in accordance with the ASCO guidelines ([Smith 2006](#)) or local/regional guidelines. Transfusions may be given in accordance with institutional policy.

After consultation with the Medical Monitor the following may be considered: hormonal or bone sparing treatment for non-B-cell malignancies, or localized radiotherapy for medical conditions other than the underlying B-cell malignancies.

Corticosteroids for non-cancer-related medical reasons at doses equivalent to ≤ 20 mg per day of prednisone or its equivalent are permitted. Corticosteroids as pre-medication for hypersensitivity reactions (e.g., CT scan pre-medication or infusion-related reaction) are also permitted. Short courses (less than 14 days) of corticosteroid treatment for non-cancer-related medical reasons (e.g., joint inflammation, asthma exacerbation, rash, antiemetic use and infusion reactions) at doses that do not exceed 100 mg per day of prednisone or equivalent are permitted. Corticosteroid treatment courses of 14 days or more may be considered after consultation with the Medical Monitor. For purposes of premedication or management of rituximab infusion reactions only, 100 mg prednisone (or its equivalent) per day may be exceeded.

COVID-19 Pandemic-Related Vaccination Guidance

Given the ongoing COVID-19 pandemic, selected non-live vaccines (e.g., mRNA, non-replicating viral vector, protein subunit, etc.) to prevent SARS-CoV-2 infection may be administered during screening, the treatment period, or follow up, as long as components of the vaccine are not contraindicated.

The decision to receive a locally available vaccine is encouraged, but should be based on local guidance and an individual discussion between the treating physician and the subject.

Any SARS-CoV-2 vaccine information must be documented on the COVID-19 vaccine details eCRF. Refer to Section [11.4.9](#) for instructions on reporting any adverse events associated with the COVID-19 vaccine.

